FDA	Food and Drug Administration
HDAC	Histone Deacetylase Inhibitors
IMiDs	Immunomodulatory drugs
MRD	Minimal Residual Disease
MM	Multiple Myeloma
nCR	Near Complete Response
Len	Lenalidomide
ORR	Overall Response Rate
PD	Progression of Disease
PR	Partial Response
Pom	Pomalidomide
PFS	Progression Free Survival
PIs	Proteasome Inhibitors
PQC	Product Quality Complaint
sCR	Stringent Complete Response
TOS	Time On Study
TTP	Time To Progression
VGPR	Very Good Partial Response

PROTOCOL SUMMARY

Study Title

A Multi-Center Phase 1b/2 Study of Daratumumab with Pomalidomide and Dexamethasone in Combination with All-Transretinoic Acid in Patients with Multiple Myeloma Previously Exposed to Daratumumab-Based Regimens.

Indication

Relapsed or refractory multiple myeloma (MM) after treatment with Lenalidomide and Daratumumab (LENDara)-based therapy.

Brief Background

Multiple Myeloma (MM) is an incurable plasma cell malignancy affecting 32,000 new patients/year and accounting for over 10,000 deaths in the US annually. Despite new advances in treatment, the disease is still characterized by a relapsing course and is invariably fatal. Nearly all patients with MM relapse eventually and become refractory to treatment. This population is particularly challenging to treat and with low survival rates due to a number of patient- and disease-related factors, including patient comorbidities, biological heterogeneity, and toxicities from prior treatments. For example, patients with MM whose disease develops resistance to bortezomib and Lenalidomide have a median OS of 9 months (Kumar et al, 2012).

Daratumumab (Dara) is a human IgG1-k monoclonal antibody to CD-38 that effectively mediates destruction of CD-38 expressing malignant plasma cells. It was approved by the Food and Drug Administration (FDA) in the United States in November 2015 as a single agent for the treatment of patients with MM who have received at least three prior therapies. CD38 serves not only as an antigen but also as an enzyme that catalyzes the metabolism of cyclic adenosine diphosphate ribose and nicotinic acid adenine dinucleotide phosphate (Lee 2006). Thus representing an important immunotherapy target due to its high expression on malignant plasma cells and low expression on other normal lymphoid and myeloid cells as well as being an important modulator of intracellular signaling (Chillemi et al, 2013).

Dara has been shown to have efficacy in combination with immunomodulatory (IMiD) agents such as lenalidomide (Len) and pomalidomide (Pom). The POLLUX trial was a randomized trial which examined the combination of Dara with Len and dexamethasone (Dex) compared to Len-Dex alone in patients relapsed or refractory multiple myeloma who had ≥ 1 prior therapy. With a median follow-up of 13.5 months, median progression free survival (PFS) had not yet been reached in the triplet combination compared to 18.4 months with Len-Dex alone (HR 0.37; 95% CI: 0.27, 0.52; $p < 0.0001$) (Dimopoulos et al, 2017). Overall response rate (ORR) with Dara-Len-Dex was 91.3%. A phase 2 single arm trial evaluated Dara with Pom and Dex in patients who had received ≥ 2 prior therapies. Overall response rate was 60% with 13.6% achieving a complete response (CR) or better (Chari et al, 2017).

Factors that determine susceptibility of MM cells to Daratumumab include levels of target antigen CD38 and expression levels of the complement inhibitory proteins CD55 and CD59. Experiments with isogenic MM cell lines expressing different levels of CD38 revealed that the level of CD38 expression is an important determinant of Dara-mediated Antibody-Dependent Cell-Mediated Cytotoxicity (ADCC), and Complement Dependent Cytotoxicity (CDC) (Nijhof et al, 2015). At time of progression, there is a reduced level of CD38 on MM cells, whereas CD55 and CD59 are increased. In a cohort of 102 patients treated with Daratumumab monotherapy, pretreatment levels of CD38 expression on MM cells were significantly higher in patients who achieved at least a partial response (PR) compared with patients who achieved less than PR. CD38 expression was reduced in both bone marrow-localized and circulating MM cells, following the first Daratumumab infusion. CD38 expression levels on MM cells were again increased following Daratumumab discontinuation. In contrast CD55 and CD59 levels were significantly increased on MM cells at the time of progression (Nijhof et al, 2016). These preclinical and clinical data indicate that the downregulation of CD38 and the upregulation of CD55 and CD59 are involved in the development of Dara-resistant multiple myeloma.

All-trans retinoic acid (ATRA) has been shown in both cell lines and primary MM samples to increase CD38 expression levels and also to reduce expression of the complement-inhibitory proteins CD55 and CD59(Nijhof et al, 2015). This resulted in significant enhancement of activity of Daratumumab in vitro and in humanized MM mouse models. Daratumumab and ATRA exhibit a strong synergy in MM cells derived from Dara-naïve patients and from patients with Dara-refractory disease, providing preclinical rationale for further evaluation of Daratumumab combined with ATRA in MM patients. Preliminary data from phase 1 trials combining Daratumumab and ATRA have shown that the combination is safe using ATRA 45 mg/m²/day dose.²⁰

It is our hypothesis that therapy with the addition of ATRA to the combination of Dara and Lenalidomide (Len) or Pomalidomide (Pom) with Dexamethasone (Dex) in patients progressing on Dara plus an IMiD + Dex will result in a significant clinical response. The aim of this study is to determine the ORR of Dara + Pom + Dex + ATRA in patients progressing on Daratumumab + Lenalidomide + Dex and to determine whether this combination is suitable for clinical use and evaluation in subsequent randomized trials. To this end, the ORR of Dara + Pom + Dex in combination with ATRA will be determined for patients relapsing on Dara + Len + Dex or Dara + Pom + Dex.

Objectives

Primary Objectives:

Phase 1b: The primary objective is to determine the safety and tolerability of the combination of Dara + Pom + Dex + ATRA.

Phase 2: To determine the ORR of the combination of Dara + Pom + Dex + ATRA in patients progressing on Dara + Len + Dex

Secondary Objectives:

- 1) To determine the ORR of the combination of Dara + Pom + Dex + ATRA in patients progressing on Dara + Pom + Dex
- 2) To determine the best stringent complete response (sCR)/CR/near CR (nCR) and >/= very good partial response (VGPR) rates.
- 3) To estimate time on study (TOS), duration of response (DOR), time to progression (TTP), progression-free survival (PFS) and overall survival (OS) distributions.
- 4) To define the toxicity using CTCAE V5 criteria.
- 5) To evaluate the status of minimal residual disease (MRD) in patients who achieve sCR, CR, or nCR.
- 6) To determine prognostic factors for PFS and OS.

Exploratory Objectives

- 1) To identify predictive factors for clinical response to Dara in combination with ATRA, Pom, and Dex.
- 2) To identify risk factors for Dara in combination with ATRA, Pom, and Dex- induced immune-related adverse events.
- 3) To correlate immune profiles (baseline, on-treatment, end of treatment, remission or PD) with ORR/PD.
- 4) To determine if any peripheral blood laboratory values during patient's routine clinical care are associated with ORR/PD or risk for treatment-related adverse events.
- 5) To correlate molecular profiles (baseline, on-treatment, end of treatment, remission or relapse) with ORR/PD.
- 6) To identify intestinal microbiota associated biomarkers that predict response and risk for development of treatment-related toxicities at baseline, on-treatment, post-treatment and relapse.

Study Endpoints

Primary Endpoints:

Phase 1b: The number of patients with treatment emergent adverse events (TEAEs) overall and per dose level.

- Patients with DLTs at each dose level.
- Patients with Grade ≥ 3 TEAEs
- Patient with serious adverse events (SAEs)
- Patients who discontinue because of TEAEs
- Patients with dose modifications (delays, interruptions, dose reductions)
- Clinically significant laboratory values

Phase 2: ORR as defined by IMWG criteria (subjects progressing on Dara + Len + Dex)

Secondary Endpoints:

- 1) ORR as defined by IMWG criteria (subjects progressing on Dara + Pom + Dex)

- 2) Rate of CR, sCR, or nCR
- 3) Rate of VGPR
- 4) TTP
- 5) DOR
- 6) PFS using Kaplan Meier method
- 7) OS using Kaplan Meier method

Exploratory Endpoints:

Explorative endpoints of samples collected before, during and after treatment with Dara + ATRA, + Pom + Dex and include but are not limited to the following:

- 1) Gut Microbiome analysis
- 2) Immune cell subset analyses
- 3) Analyses of cytokine, chemokine, inflammatory/anti-inflammatory and bacterial translocation markers
- 4) Basic peripheral blood laboratory variables
- 5) Genetic and epigenetic profiles

Study Design

This is a multi-institution phase 1b/2 study of ATRA in combination with fixed dose Daratumumab, Pomalidomide and Dex for patients with relapsed multiple myeloma who have progressed on the combination of Dara + Len + Dex. During the dose escalation phase (phase 1b) and after the first cycle, patients who have not experienced a drug-limiting toxicity (DLT), have not shown signs of progressive disease (PD), and in the opinion of the investigator would continue to benefit from additional Dara + Pom + Dex + ATRA may receive additional cycles of treatment (see section 7.4 for details). The phase 2 portion will allow further enrollment at the maximum tolerated dose (MTD) to further evaluate safety and efficacy.

Study Population

Patients with relapsed or refractory multiple myeloma who have progressed on the combination of Dara + Len + Dex or Dara + Pom + Dex. We will include a maximum of 42 patients (among 20-32 subjects previously exposed to Dara + Len + Dex or 10-22 subjects previously exposed to Dara + Pom + Dex).

Length of Study

The overall study duration is expected to be three (3) years, two years for enrollment, one year to complete follow-up.

Treatment Plan

During 28-day treatment cycles, patients will receive Dara 1800 mg subcutaneous (SC) administration at their current dose upon enrollment onto the study depending on their cycle. (If they are on cycles 1-2

then they will receive Dara 1800 mg SC days 1,8,15,22; if they are on cycles 3-6 they will receive Dara 1800 mg SC days 1 and 15; if they are on cycle 7 or beyond they will receive Dara 1800 mg SC on day 1).

Pomalidomide will be administered at the patient's currently tolerated dose (4,3, or 2 mg po daily) on days 1-21. Patients who are progressing on daratumumab + lenalidomide + dexamethasone will start with the 4 mg dose (standard of care starting dose) of pomalidomide.

Dexamethasone will be administered at 40 mg once weekly on days 1,8,15 for patients 75 years old and younger and at 20 mg once weekly on days 1,8,15 for patients older than 75. Patients may stay on their currently administered steroid regimen if it does not match the above.

For the Phase 1b portion, ATRA will be escalated as follows: 35.5 mg/m²/day, then 45mg/m²/day (see section 7.4 for details). The first administration of ATRA will be given in the morning, two days before the scheduled Dara infusion. The last administration of ATRA will be given in the evening of the day that Dara was administered (days -2, -1, and 0; day 0 is the day of Dara infusion).

Treatment repeats every 28 days for at least 8 cycles in the absence of disease progression or unacceptable toxicity. Patients achieving stable disease may continue to receive treatment in the absence of disease progression or unacceptable toxicity.

After completion of the study treatment, patients are followed up at 28 days and then every 3 months for up to 12 months. Subjects will be evaluated for disease response during each cycle and at the end of study.

Key Inclusion Criteria

1. Documented multiple myeloma with prior exposure to an immunomodulatory agent (IMiD), proteasome inhibitor (PI), and monoclonal antibody to CD-38 (CD-38 mo-Ab).
2. Patients must have 2 or more prior lines of therapy.
3. Patients must have been previously exposed to:
 - a. Dara+Len+Dex and must have achieved at least stable disease to this combination.
or;
 - b. Dara + Pom + Dex and must have achieved at least stable disease to this combination.
4. Histologically confirmed and relapsed multiple myeloma with measurable disease, defined by at least one of the following:
 - a. Serum monoclonal protein ≥ 0.5 g/dL;
 - b. Monoclonal protein in the urine on 24-hour electrophoresis ≥ 200 mg;
 - c. Serum immunoglobulin free light chain (FLC) ≥ 10 mg/dL (100 mg/L) provided serum FLC ratio is abnormal;
 - d. New or progressing biopsy proven plasmacytoma on exam or imaging; or
 - e. Bone marrow plasma cells $\geq 20\%$;
5. Cycle 1 day 1 of study treatment must be within 3 months of last exposure to Daratumumab.
6. Life expectancy >3 months
7. ECOG PS 0-2
8. Age ≥ 18

9. Adequate organ function, including bone marrow, renal, hepatic, pulmonary, and cardiac function based on the last assessment performed within the Screening Period, defined as:
 - a. Absolute neutrophil count (ANC) $\geq 1,000/\mu\text{L}$;
 - b. Platelet count $\geq 50,000/\mu\text{L}$, ($\geq 30,000/\mu\text{L}$ if bone marrow plasma cells are $\geq 50\%$ of cellularity);
 - c. Hemoglobin $\geq 7.5\text{g/dL}$;
 - d. Creatinine clearance $\geq 60\text{ mL/min}$ (assessed as glomerular filtration rate using the Cockcroft-Gault formula);
 - e. Alanine aminotransferase or aspartate aminotransferase $\leq 2.5 \times$ upper limit of normal (ULN);
 - f. Total bilirubin $\leq 1.5 \times$ ULN (except for patients with Gilbert's syndrome confirmed by UGT1A1 mutation);
 - g. Left ventricular ejection fraction $\geq 50\%$ as assessed by echocardiography or multi-gated acquisition (MUGA) scan; and
 - h. Must have a minimum level of pulmonary reserve defined as Grade <2 dyspnea and pulse oxygenation $\geq 92\%$ on room air;

10. Prior to first dose of study drug, a woman must be either:

- Not of childbearing potential: premenarchal; postmenopausal (>45 years of age with amenorrhea for at least 12 months or any age with amenorrhea for at least 6 months and a serum follicle stimulating hormone level $>40\text{ IU/L}$ or mIU/mL); permanently sterilized (eg, bilateral tubal occlusion [which includes tubal ligation procedures as consistent with local regulations], hysterectomy, bilateral salpingectomy, bilateral oophorectomy); or otherwise be incapable of pregnancy
- Of childbearing potential and practicing 2 highly effective methods of birth control at time of informed consent and will continue through study and for at least one month after final dose of study drug. Must be consistent with local regulations regarding the use of birth control methods for subjects participating in clinical studies: e.g., established use of oral, injected or implanted hormonal methods of contraception; placement of an intrauterine device or intrauterine system; barrier methods: condom with spermicidal foam/gel/film/cream/suppository or occlusive cap (diaphragm or cervical/vault caps) with spermicidal foam/gel/film/cream/suppository; male partner sterilization (the vasectomized partner should be the sole partner for that subject); true abstinence (when this is in line with the preferred and usual lifestyle of the subject)

Note: If the childbearing potential changes after start of the study (e.g., woman who is not heterosexually active becomes active, premenarchal woman experiences menarche)

- A woman must begin 2 highly effective methods of birth control, as described above, and must not donate eggs during the study and for at least three months after final dose of study drug.

11. A woman of childbearing potential must have 2 negative serum (β human chorionic gonadotropin) or urine pregnancy tests during screening, the first one within 28 days prior to the first dose of study drug and the second within 24 hours prior to the first dose of study drug.
12. A man who is sexually active with a woman of childbearing potential and has not had a vasectomy must agree to use a barrier method of birth control e.g., either condom with spermicidal foam/gel/film/cream/suppository or partner with occlusive cap (diaphragm or cervical/vault caps) with spermicidal foam/gel/film/cream/suppository, and all men must also not donate sperm during the study and for 3 months after receiving the last dose of study drug.
13. Subjects must be willing and able to adhere to the prohibitions and restrictions specified in this protocol and referenced in the informed consent form (ICF).

Key Exclusion Criteria

1. Major concurrent illness or organ dysfunction
2. Active GVHD requiring systemic corticosteroids in a subject who previously received allogeneic-SCT.
3. Cord compression or CNS involvement
4. Recent/Prior active malignancy requiring active therapy 2 years prior to enrollment excluding non-melanoma skin cancer.
5. Prior life-threatening hypersensitivity to daratumumab or an IMiD
6. Plasma cell leukemia
7. Pregnant or lactating females
8. Men donating sperm during study
9. Seropositive for human immunodeficiency virus (HIV)
10. Seropositive for hepatitis B (defined by a positive test for hepatitis B surface antigen [HBsAg]).
Subjects with resolved infection (ie, subjects who are HBsAg negative but positive for antibodies to hepatitis B core antigen [anti-HBc] and/or antibodies to hepatitis B surface antigen [anti-HBs]) must be screened using real-time polymerase chain reaction (PCR) measurement of hepatitis B virus (HBV) DNA levels. Those who are PCR positive will be excluded. EXCEPTION: Subjects with serologic findings suggestive of HBV vaccination (anti-HBs positivity as the only serologic marker) AND a known history of prior HBV vaccination, do not need to be tested for HBV DNA by PCR
11. Seropositive for hepatitis C (except in the setting of a sustained virologic response [SVR], defined as aviremia at least 12 weeks after completion of antiviral therapy)
12. Chronic obstructive pulmonary disease (COPD) with a Forced Expiratory Volume in 1 second (FEV1) less than 50% of predicted normal
13. Moderate or severe persistent asthma within the past 2 years, or uncontrolled asthma of any classification. Note that participants who currently have controlled intermittent asthma or controlled mild persistent asthma are allowed to participate
14. History of prolonged QTc > 480ms or ventricular arrhythmia on screening EKG or history of ventricular arrhythmia QTc or ventricular arrhythmia
15. Myocardial infarction within 6 months before randomization, or unstable or uncontrolled disease/condition related to or affecting cardiac function (e.g., unstable angina, congestive heart failure, New York Heart Association Class III-IV)
16. Received any prior anti-myeloma therapy within 14 days of planned study treatment

Statistical Considerations:

Brief Statistical Rationale

The phase 1b will estimate the maximum tolerated dose (MTD) by a standard 3+3 design using data collected in the dose escalation phase. MTD will be defined for each dosing level. A maximum of 2 dose levels are planned (35.5 mg/m²/day to 45 mg/m²/day). For phase 1b the number of evaluable patients is planned to be 12.

The phase 2 portion will evaluate the clinical activity of Dara + Pom + Dex + ATRA. A Simon's two-stage minimax design will be used. The null hypothesis that the true response rate is $\leq 30\%$ will be tested against a one-sided alternative of 50% or higher at the one-sided type I error of 0.10 at 80% power. In the first stage, 12 patients will be accrued. If there are 4 or fewer responses in these 12 patients, the study will be stopped due to futility. Otherwise, 16 additional patients will be accrued for a total of 28. The null hypothesis will be rejected if 12 or more responses are observed in 28 patients.

Adverse events (AEs) will be summarized by treatment group and overall. Categorical variables such as ORR will be tabulated by treatment group and overall. Time to event variables will be analyzed using Kaplan-Meier survival curves and Kaplan-Meier medians will be provided.

Statistical Power Calculations

This Simon's two-stage design yields a type I error rate of 0.095 and power of 0.802 when the true response rate is 48%. The probability of early stopping due to futility is approximately 49.2%.

Primary Analysis

After a maximally 42 patients are enrolled in the phase 1b and phase 2 portions combined, a primary interim efficacy analysis and the second safety analysis will be conducted. The subset safety analysis will be also descriptively performed based on the previous exposure groups (Dara + Len + Dex or Dara + Pom + Dex).

Overall response rate (ORR) and stringent complete response (sCR)/CR/near CR (nCR) according to IMWG criteria will be determined and corresponding 2-sided 80% exact binomial confidence interval will be calculated. The subset ORR analysis will be also performed based on the previous exposure groups (Dara + Len + Dex or Dara + Pom + Dex).

The Kaplan-Meier (KM) method will be used to estimate the time-to-event endpoints such as time on study (TOS), duration of response (DOR), time to progression (TTP), progression-free survival (PFS) and overall survival (OS) distributions. The subset time-to-endpoint outcome analysis will be also performed using the KM method based on the previous exposure groups (Dara + Len + Dex or Dara + Pom + Dex).

Adverse events and tolerability from all subjects who receive at least one dose of study drug will be evaluated for safety and tolerability. Data will be tabulated to examine the frequency.

Study Sites

1. Hackensack University Medical Center - John Theurer Cancer Center - Hackensack, NJ
2. Georgetown-Lombardi Cancer Center - Washington, DC

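### The synopsis futility rule (stop at 4 or fewer of 12) does not give its stated properties: power is 73% at a 50% response rate, not 80.2%, and early stopping under the null is 72%, not 49.2%

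*Combined protocol and SAP*

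**What the plan says.** The Protocol Summary, under Statistical Considerations (Brief Statistical Rationale), sets out the phase 2 design. It states "A Simon's two-stage minimax design will be used", and that a null response rate of 30% or less "will be tested against a one-sided alternative of 50% or higher at the one-sided type I error of 0.10 at 80% power". Stage 1 has 12 patients. The futility rule is "If there are 4 or fewer responses in these 12 patients, the study will be stopped due to futility". Otherwise 16 more patients are enrolled, for 28 in total, and the null is rejected at 12 or more responses.

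The next paragraph, Statistical Power Calculations, gives the properties of this design: "This Simon's two-stage design yields a type I error rate of 0.095 and power of 0.802 when the true response rate is 48" per cent, and "The probability of early stopping due to futility is approximately 49.2" per cent.

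The body of the protocol describes something else. Sections 4.1, 9.2 and 9.5 have a first stage of 10 patients that stops at 2 or fewer responses. Section 9.2 adds a total of 20 patients, rejection at 8 or more responses, and a test of 25% against 48%.

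**The concern.** Two things do not fit on a first reading. The design is set up against an alternative of 50%, but the power is quoted at 48%, which is the alternative in Section 9.2. And with 12 patients and a 30% rate the expected number of responses is 3.6, so a rule that stops at 4 or fewer should stop well over half the time under the null, not 49.2%.

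The boundary decides whether phase 2 continues. At 4 responses in 12 (33%) the written rule ends the study, while the design whose properties are quoted would go on to 28 patients. If the written rule is applied, an active combination is abandoned more often than the stated power implies, and the 80% power target is missed.

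**Working it through.** **Inputs** (Protocol Summary, Statistical Considerations): p0 = 0.30; p1 = 0.50; one-sided alpha 0.10; power 0.80; n1 = 12; n = 28; reject at 12 or more responses; written futility boundary r1 = 4. Stated results: 0.095; 0.802 at 48%; 49.2%.

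**Formulas.** Let X1 be the number of stage 1 responses, binomial (12, p), and X2 the number of stage 2 responses, binomial (16, p).

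- Early stopping: PET(p) = P(X1 ≤ r1).
- Rejection: R(p) = sum over x from r1 + 1 to 12 of P(X1 = x) × P(X2 ≥ 12 − x). This is the type I error at p = 0.30 and the power at the alternative.

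**Step 1: find the design that gives the stated figures.** With r1 = 3, R(0.30) = 0.0954, R(0.50) = 0.8020 and PET(0.30) = 0.4925. These are the three stated values, provided the power is read at 50%. A search for the minimax design at 30% against 50%, alpha 0.10 and power 0.80 returns the same design: stop at 3 or fewer of 12, reject at 12 or more of 28.

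**Step 2: evaluate the rule as written.**

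| Quantity | Stated | r1 = 4 (written) | r1 = 3 |
|---|---|---|---|
| Type I error at 30% | 0.095 | 0.0782 | 0.0954 |
| Power at 50% | – | 0.7297 | 0.8020 |
| Power at 48% | 0.802 | 0.6653 | 0.7404 |
| Early stopping at 30% | 49.2% | 72.37% | 49.25% |
| Early stopping at 50% (wrongful) | – | 19.38% | 7.30% |

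**Step 3: check the one-response shift by hand.** The two boundaries differ only in what happens at X1 = 4.

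- Under the null, P(X1 = 4) = 495 × 0.30^4 × 0.70^8 = 0.231, and 0.4925 + 0.231 = 0.724, the early-stopping figure for the written rule.
- At 50%, P(X1 = 4) = 495/4096 = 0.1208 and P(X2 ≥ 8) = 0.5 + 0.5 × 12870/65536 = 0.598. Their product is 0.072, which equals the power lost: 0.8020 − 0.7297 = 0.0723.

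**Step 4: separate the two errors at 48%.** The gap between the stated 0.802 and the actual 0.6653 is 0.137. Of this, 0.802 − 0.7404 = 0.062 comes from quoting power at the wrong rate and 0.7404 − 0.6653 = 0.075 from the boundary.

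**Step 5: ask whether any 28-patient design could have 80% power at 48%.** A search for 30% against 48% at alpha 0.10 and power 0.80 finds no solution below n = 34. The 48% sentence therefore cannot be right for 28 patients, whatever the boundary.

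**Step 6: expected sample size under the null**, 12 + 16 × (1 − PET). With r1 = 4 it is 12 + 16 × 0.2763 = 16.4; with r1 = 3 it is 12 + 16 × 0.5075 = 20.1.

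**The case against.** The strongest reply is that the synopsis rule may never be used. Sections 4.1, 9.2 and 9.5 agree on a first stage of 10 patients, and the Section 9.2 design comes close to its own stated properties: recomputed type I error 0.0956, power 0.8059 at 48% and early stopping 52.6%, against 0.096, 0.806 and 52.0% stated. If the body governs, the error sits in a leftover paragraph, and the larger problem is that the document carries two phase 2 designs.

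That is a fair limit on the consequence, but it does not remove the error. Nothing in the documents says which design prevails, and the synopsis is current text. Its size also fits the planned maximum of 42 patients better: 12 in phase 1b plus 28 is 40, whereas 12 plus 20 is 32.

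Three further points stand as qualifications. The written rule keeps the type I error below 0.10, so it does not add false positives. The rise in wrongful stage 1 stops overstates the net loss, because some trials that continue from 4 of 12 would fail at the final analysis; the net cost at 50% is about 7 points of power. And part of the shortfall at 48% comes from the mislabelled rate, as Step 4 shows.

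**Conclusion.** Wrong as written. The stated boundary gives none of the stated properties. Early stopping under the null is about 23 points higher than stated (72.4% against 49.2%). At a true rate of 50% the trial would miss an active combination 27.0% of the time (1 − 0.7297), against the 19.8% implied by the stated power (1 − 0.802); at 48% the figure is 33.5% (1 − 0.6653). Wrongful futility stops at 50% rise about 2.7-fold (19.4% against 7.3%).

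The results are exact and assume only independent responses with a common rate and the decision rules as printed. That the boundary should be 3 and the rate 50% is well supported, because together they recover all three stated figures. That the 48% came from Section 9.2 is an inference. The practical effect depends on the synopsis design being the one that is run.

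**What to change.** Decide first which phase 2 design governs, before the stage 1 decision.

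- **If the 12/28 design is kept:** change the futility boundary to 3 or fewer responses in 12, and state the power of 0.802 at a true response rate of 50%. The other stated figures can stay. Sections 4.1, 9.2 and 9.5 must then be rewritten to match.
- **If the Section 9.2 design is kept:** delete the 12/28 design and its operating characteristics from the Protocol Summary.

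Within the summary the first option is two wording changes and needs no change to the 12 or 28 patients. Compared with the written rule, expected sample size under the null rises from 16.4 to 20.1 patients, which the stated 49.2% early-stopping probability already implies. The wider cost is the alignment of the three body sections.
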